12.1 Study Design/Endpoints

The study is a randomized placebo-controlled trial. The primary outcome measure will be change score on the FACIT-fatigue subscale from randomization to the end of the study. Exploratory endpoints include changes in sleep continuity (sleep efficiency, total sleep time, sleep latency), quality-of-life measures, depression, anxiety, and subjective cognitive function.

Analysis of both the primary and exploratory endpoints will be by modified intention to treat. The mITT analysis (for both primary and exploratory endpoints) will be a per-protocol analysis; only patients who complete the entire trial according to the protocol will be counted towards the final results.

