5.5 Duration of Therapy

Duration of therapy will be five weeks. In the absence of adverse event(s), treatment will continue for the entire five weeks unless one of the following criteria applies:

- Initiation of opioid-containing medications
- Intercurrent illness that prevents further administration of treatment
- Unacceptable adverse event(s)
- Participant demonstrates an inability or unwillingness to comply with the oral medication regimen and/or documentation requirements
- Participant decides to withdraw from the study
- General or specific changes in the participant's condition render the participant unacceptable for further treatment in the judgment of the treating investigator

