12. STATISTICAL CONSIDERATIONS

Entry criteria of a drop of 10 points on FACIT-fatigue subscale was selected because a change of 10 points has been shown to constitute a clinically meaningful difference on this subscale⁵³. The effect of naltrexone (and placebo in the control group) will be defined as a difference (in raw FACIT score) between the pre-randomization FACIT and the follow-up FACIT. FACIT-fatigue subscale scores are normally distributed in anemic and nonanemic cancer populations⁴², with a standard deviation of 10 points. Setting power as 0.8, and significance as 0.05, assuming a two-sided type I error, 122 patients per arm are required to detect a “difference of a difference” of at least 3.6 points on FACIT-fatigue. The 3.6 point difference was selected because it is the approximate mean of prior effect sizes utilizing FACIT-fatigue in clinical trials of erythropoietin or darbopoeitin vs. placebo. Assuming a 20% drop-out rate, approximately 150 patients per arm will be randomized.

An interim analysis will be conducted on one occasion, after collecting data for the first 75 patients in each arm. This analysis will be conducted in light of several possibilities: 1) the observed benefit of naltrexone is so promising that it would be unethical not to use it for all eligible patients, 2) the observed rate of side effects/toxicity is too high, 3) futility –it appears to be unlikely that there is a clinically significant difference between the naltrexone and placebo arms. The Haybittle–Peto boundary rule (with 0.001 significance threshold) will be employed to determine whether the trial should be stopped early. The final analysis will still use the 0.05 threshold of significance.

Futility testing will also be performed on the primary outcome at a low level (one-sided alpha 0.0025) on one occasion (after the first 75 patients are enrolled).

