12.4 Analysis of Secondary Endpoints

Secondary (exploratory) endpoints (changes in sleep continuity (sleep efficiency, total sleep time, sleep latency), quality-of-life measures, depression, anxiety, and subjective cognitive function) will be analyzed by modified intention to treat. Since no pre-existing data describes the magnitude of associations of our exploratory outcomes with naltrexone use in this population, we are unable to speculate on the statistical power required to detect an effect. Any relevant associations and their statistical significances will be calculated using descriptive statistics. In addition, radiation therapy status (currently receiving RT vs. recently completed RT) will be included as a covariate in the multivariate analysis.

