12.5.2 Evaluation of Response

All of the participants who meet the eligibility criteria, consent to randomization, and complete the entire treatment protocol will be included in the main analysis of effect.

For all dropouts, we will use an off-study form in order to obtain information about the reasons for not completing the study. We will use this information for post-hoc analyses to lessen the chance of bias due to missing data.

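### The primary analysis is called modified intention to treat but counts only per-protocol completers, and no efficacy analysis of all randomised participants is pre-specified

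*Combined protocol and SAP*

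**What the plan says.** Section 12.1 gives the primary outcome as the "change score on the FACIT-fatigue subscale from randomization to the end of the study". It says primary and exploratory endpoints are analysed by modified intention to treat and then defines the term: "The mITT analysis (for both primary and exploratory endpoints) will be a per-protocol analysis", so that "only patients who complete the entire trial according to the protocol will be counted towards the final results".

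Section 12.5.2 confirms this. Participants who are eligible, consent to randomisation and "complete the entire treatment protocol will be included in the main analysis of effect". Section 12.4 carries the label to the secondary endpoints, which "will be analyzed by modified intention to treat".

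For drop-outs, 12.5.2 provides an off-study form recording reasons and adds: "We will use this information for post-hoc analyses to lessen the chance of bias due to missing data". No method or population is given. The all-participants rule in 12.5.1 concerns toxicity only. The missing-data note printed with the FACIT-F form concerns questionnaire scoring.

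The sample size in section 12 anticipates the loss: "Assuming a 20% drop-out rate, approximately 150 patients per arm will be randomized".

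**The concern.** The label and the definition contradict each other. A reader who sees mITT expects nearly all randomised participants in their assigned arms; the definition delivers completers.

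The larger problem is the definition. Whether someone completes is settled after randomisation. Sections 5.5 and 5.7 end treatment or participation for adverse events, opioid use, significant deviation, drug held for more than three days, and non-compliance ("Participant demonstrates an inability or unwillingness to comply with the oral medication regimen and/or documentation requirements"). Naltrexone can affect several of these. The only pre-specified efficacy result therefore compares those who managed to finish on naltrexone with those who managed to finish on placebo.

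The bias could go either way. If more stop on naltrexone and stoppers have worse fatigue, completers flatter the drug. Section 2.2 notes that this fatigue improves spontaneously after radiotherapy; if stoppers are people who have recovered, completers count against the drug. With no all-randomised result, a reader cannot tell which applies.

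**Working it through.** **Inputs from section 12.** SD 10, difference 3.6, two-sided 5%, power 80%, 20% drop-out, 150 per arm. All calculations use the normal approximation.

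**The plan's own figure.** n = 2 × (1.960 + 0.842)² × 10² / 3.6² = 121.1, rounded up to the stated 122 per arm. Then 122 / 0.8 = 152.5, close to the stated 150. At 20% drop-out, 150 × 0.8 = 120 complete per arm, so 2 × 30 = 60 of 300 do not. For 120 per arm, SE = 10 × √(2/120) = 1.29 and power is 79.6%. The arithmetic is sound, but it is built for completers.

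**Bias of the completer comparison.** Let p1 and p0 be the stopping proportions on naltrexone and placebo, and let stoppers' mean change be D points worse than that of completers in the same arm. An arm's overall mean is its completer mean minus pD. With no true effect the overall means are equal, so the completer difference is (p1 − p0) × D. SE = 10 × √(1/n1 + 1/n0), with n1 = 150(1 − p1) and n0 = 150(1 − p0). The stopping imbalance and D (3 to 10 points) are assumptions; the documents give neither.

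| Stopping, naltrexone vs placebo | Completers | Bias (points) | Share of 3.6 | Two-sided error |
|---|---|---|---|---|
| 20% vs 20% | 120 / 120 | 0 | 0% | 5.0% |
| 22.5% vs 17.5% | 116.25 / 123.75 | 0.15–0.50 | 4–14% | 5.2–6.7% |
| 25% vs 15% | 112.5 / 127.5 | 0.3–1.0 | 8–28% | 5.6–12.1% |

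If stoppers are instead 3 to 10 points better and the true effect is 3.6, the completer difference at 22.5% vs 17.5% is 3.45 to 3.10, and power falls from 79.6% to between 76.1% and 67.0%.

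**What removes the bias.** Take a repeated-measures model using weeks 1 and 5, with a share q of stoppers' week 5 scores obtained. The remaining bias is about D × [h(p1) − h(p0)] × (1 − r × g), where h(p) = p(1 − p)(1 − q) / (1 − p + pq), r is the week 1 to week 5 correlation (assumed 0.4–0.8) and g is the share of the gap already visible at week 1 (assumed 0–0.5). At 25% vs 15%:

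- q = 0: 0.18–1.0 points
- q = 0.5: 0.07–0.38 points
- q = 0.8: 0.02–0.13 points
- q = 1: none

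The model alone removes at most r × g = 0.8 × 0.5 = 40%. Obtaining the scores removes most of the rest.

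**Power of the all-randomised analysis.** Assume 150 per arm, 20% stopping, week 5 scores obtained, and stoppers keeping a share k of the effect. The average effect is 3.6 × (0.8 + 0.2k): 3.60, 3.42, 3.24 and 2.88 points for k = 1, 0.75, 0.5 and 0. Taking SD 10 within completers and within stoppers, the pooled SD is √(100 + 0.2 × 0.8 × D²). Each cell gives power, then the number per arm for 80% power.

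| D (pooled SD) | k = 1 | k = 0.75 | k = 0.5 | k = 0 |
|---|---|---|---|---|
| 0 (10.0) | 87.7%, 122 | 84.2%, 135 | 80.1%, 150 | 70.3%, 190 |
| 5 (10.2) | 86.4%, 126 | 82.7%, 140 | 78.6%, 156 | 68.6%, 197 |
| 10 (10.8) | 82.5%, 141 | 78.5%, 156 | 74.1%, 174 | 63.9%, 220 |

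Power matches the completers' 79.6% when stoppers keep about 47%, 56% or 82% of the effect in the three rows. Baseline adjustment, which could help, is not credited.

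**The case against.** The strongest reply is that the damage is unproven. No drop-out by arm is given. The 5% nausea discontinuation in section 6.1 comes from alcohol-dependence trials and has no placebo rate beside it. Under the milder imbalance the error barely moves, and a 10-point gap is a full SD. All of this stands: the figures illustrate and do not predict. The finding rests on the definition of the analysis set.

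Second, section 5.6 plans follow-up to four weeks after treatment, and beyond study end for those removed for adverse events, so some scores might exist anyway. This narrows the gap without closing it. FACIT-F is not named there, and 5.7, 5.8 and 12.5.1 take participants off the study, not merely off drug.

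Third, the documents often use trial or study for the five-week treatment period (sections 1.1, 2.2 and 5.3), so the completer wordings in 12.1 and 12.5.2 may mean the same set. That is a fair reading. But sections 1.1 and 9 schedule a week 9 FACIT-F, and someone who finishes drug but misses week 9 could be counted under one wording and not the other. This needs clarifying but is a side issue.

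Fourth, the power table depends on where SD 10 applies. If it describes all randomised participants, all-randomised power is 87.7%, 84.2%, 80.1% and 70.3% whatever D is, and completer power is 81.2% (D = 5) or 86.1% (D = 10). The break-even shares are therefore approximate.

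Finally, 60 is the planned number of drop-outs; protocol deviators who stay in could add to the exclusions.

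**Conclusion.** The concern holds and must be fixed. The plan mislabels a completer analysis, makes it the only pre-specified efficacy comparison, and leaves drop-outs to undefined post-hoc work. About 60 of 300 randomised participants are expected to fall outside it.

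The direction and size of the bias cannot be known from the documents. In the scenarios above it runs from nothing (equal stopping, equal gap) to 1.0 point of the 3.6-point target. The conclusion does not depend on those scenarios. It rests on the text of 12.1 and 12.5.2 and on the fact that completion is a post-randomisation event that treatment can influence.

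**What to change.** 1. **Population.** In 12.1, 12.4 and 12.5.2, make the primary analysis all randomised participants in their assigned arms, by a likelihood-based repeated-measures model or by ANCOVA with multiple imputation on FACIT-F. Keep the completer analysis as a per-protocol sensitivity analysis with one definition, and drop the mITT label.
2. **Data after stopping.** Keep collecting the scheduled FACIT-F once study drug has stopped, where the participant agrees. Reconcile 5.6, 5.7, 5.8 and 12.5.1 so that coming off drug is distinct from ending data collection. No treatment-stopping rule changes. This step does most of the work and belongs with step 1.
3. **Time point.** State it. Week 5 is assumed here because section 1.1 assigns outcome assessment to that visit. Reconcile it with the end-of-study wording in 12.1 and the week 9 FACIT-F. If week 9 is meant, the model and data collection must reach it.
4. **Optional.** Add a delta-adjusted sensitivity analysis, and state how scores after opioid start or unblinding (section 6.1) are handled.

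The cost is edits to those sections, the power paragraph in section 12 and, if needed, the section 9 calendar, plus a 13-item questionnaire at visits already scheduled. The real downside is power: at 150 per arm it ranges from 63.9% to 87.7% in the table above, so the sample size should be restated with an explicit assumption about the effect stoppers retain. The change should be made before unblinding, since an all-randomised analysis chosen afterwards would be post hoc and scores not collected cannot be recovered.

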12.2 Sample Size/Accrual Rate

Sample size for the intervention phase of the study is 150 patients per arm randomized to treatment. Assuming a 4 year study duration, and 2 study sites, we will randomize 1-2

participants per study site every 2 weeks (~75 randomized participants / year). The sample size for the monitoring phase of the study is not fixed, but using a conservative estimate of 30% for radiation treatment-emergent fatigue, we will need to screen 3-6 participants per study site per 2 weeks (~225 screened participants / year).

12.3 Stratification Factors

Patients will be stratified according to whether or not they received chemotherapy.

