1.2 Primary Objectives

To determine the effect of naltrexone on treatment-emergent fatigue during radiation therapy for breast cancer. The primary comparison is between changes in fatigue scores in the naltrexone-versus the placebo-treated participants as measured by the FACIT-F subscale.

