radiation-related fatigue in cancer patient populations who are not expected to require opioid therapy. Breast cancer patients receiving radiotherapy represent an important population to study because fatigue develops commonly during radiotherapy and concurrent therapy with opioids is rare. Notably, existing literature provides widely variable estimates (38-75%) of the prevalence of breast radiotherapy-emergent fatigue^{11,12} as well as differing evidence as to the most important predictors of fatigue in this population. Longitudinal studies have found that fatigue levels gradually increase during a course of breast radiotherapy, particularly during the first four weeks of treatment.¹³⁻¹⁵ Several studies have investigated clinical correlates of radiation-related fatigue in this population. Donovan found that patients (N=134) pre-treated with chemotherapy reported less fatigue during radiotherapy as compared to patients who did not receive chemotherapy, and that demographic and disease-related variables did not predict the extent of fatigue; however, psychological variables were not examined in this study.¹⁶ Manir described anemia as the most important predictor of fatigue (N=72)¹² whereas other studies have found no relationship between hemoglobin levels and fatigue.¹³ Recently, Taunk compared different radiotherapeutic regimens for early-stage breast cancer (overall N=80) and suggested that partial breast irradiation may reduce fatigue as compared to hypofractionated and standard whole breast irradiation.¹⁷ However, in the largest cohort study to date (N=250), Reidunsdatter identified medical comorbidity as a more important determinant of increased fatigue during breast radiotherapy than radiotherapy type.¹⁸ By contrast, Courtier reported that anxiety, elevated pre-treatment fatigue, and diagnoses other than invasive ductal carcinoma (e.g. DCIS or lobular subtypes) predicted radiation-emergent fatigue (N=100).¹¹ More study of the clinical correlates and course of fatigue during radiotherapy is warranted in the breast cancer population given the relatively small sample sizes, variable inclusion of relevant medical and psychosocial variables in models to predict fatigue, and conflicting findings to date. The monitoring phase of the present study offers an embedded opportunity to analyze the course, predictors, and correlates of radiotherapy-related fatigue in a controlled breast cancer population.

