4.3 Registration Process for DF/HCC and DF/PCC Institutions

The QACT registration staff is accessible on Monday through Friday, from 8:00 AM to 5:00 PM Eastern Standard Time. In emergency situations when a participant must begin treatment during off-hours or holidays, call the QACT registration line at [contact] and follow the instructions for registering participants after hours.

The registration procedures are as follows:

- Obtain written informed consent from the participant prior to the performance of any protocol specific procedures or assessments.
- Complete the QACT protocol-specific eligibility checklist using the eligibility assessment documented in the participant's medical record and/or research chart. **To be eligible for registration to the protocol, the participant must meet all inclusion and exclusion criterion as described in the protocol and reflected on the eligibility checklist.**

Reminder: Confirm eligibility for ancillary studies at the same time as eligibility for the treatment protocol. Registration to both treatment and ancillary protocols will not be completed if eligibility requirements are not met for all studies.

- Fax the eligibility checklist(s) and all pages of the consent form(s) to the QACT at [contact]. For Phase I protocols, attach participant dose level assignment confirmation from the sponsor.
- The QACT Registrar will (a) review the eligibility checklist, (b) register the participant on the protocol, and (c) randomize the participant when applicable. The randomization will be a block randomization at each site (DFCI/BWH vs MGH).
- An email confirmation of the registration and/or randomization will be sent to the Overall PI, study coordinator(s) from the Lead Site, treating investigator and registering person immediately following the registration and/or randomization.

[figure not shown]

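### Sections 4.3 and 12.3 each name one randomisation factor without mentioning the other, and the primary FACIT-F comparison names neither; stating one scheme and adjusting for both is a small, nearly free gain

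*Combined protocol and SAP*

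**What the plan says.** Section 12.3 is a single sentence: "Patients will be stratified according to whether or not they received chemotherapy". It does not name site, and it does not say whether the stratification applies to the allocation list, the analysis, or both.

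Section 4.3, the procedure the registrar carries out, says: "The randomization will be a block randomization at each site (DFCI/BWH vs MGH". It names neither chemotherapy nor a block size.

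The primary comparison is given in Section 1.2 ("The primary comparison is between changes in fatigue scores in the naltrexone-versus the placebo-treated participants as measured by the FACIT-F subscale") and Section 12.1 ("The primary outcome measure will be change score on the FACIT-fatigue subscale from randomization to the end of the study"). Section 10 and the opening of Section 12 define the effect as a raw change in score. None of these names a test, a model or a covariate.

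The one covariate assigned to a treatment analysis appears under secondary endpoints in Section 12.4: "radiation therapy status (currently receiving RT vs. recently completed RT) will be included as a covariate in the multivariate analysis". Section 9 lists candidate covariates for the course of fatigue, but chemotherapy and site are not among them.

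Section 2.1 gives a reason to care about chemotherapy. It cites a cohort of 134 in which patients "pre-treated with chemotherapy reported less fatigue during radiotherapy as compared to patients who did not receive chemotherapy". The size of that difference is not given.

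**The concern.** Two things are left open.

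The first is the allocation list. Section 4.3 is the operational text. Someone building the list from it would produce blocks within site, and the chemotherapy balance that Section 12.3 calls for would be left to chance.

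The second is the analysis. When randomisation is balanced on a factor that predicts the outcome, the between-arm difference varies less than a simple two-sample standard error says. A test that ignores the factor then runs below its nominal level and gives up some power. If the factor was not balanced, an unadjusted comparison leaves any chance imbalance in the estimate, and adjustment would remove it.

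Sections 12.1 and 12.5.2 also restrict the main analysis to patients who complete the protocol. Balance built at randomisation need not survive in that subset, so a covariate named in advance is useful however the list was built.

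**Working it through.** **The plan's own figure.** Inputs from Section 12: difference 3.6 points, SD 10, two-sided alpha 0.05, power 0.80 ("Setting power as 0.8, and significance as 0.05, assuming a two-sided type I error, 122 patients per arm are required to detect" a difference "of at least 3.6 points on FACIT-fatigue").

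n per arm = 2 × [10 × (1.960 + 0.842) / 3.6]² = 121.1, rounded up to 122. Power at 122 is 0.803. Allowing for 20% dropout, 122 / 0.8 = 152.5, so 153; the plan's approximate 150 is within 3%. The stated size is therefore that of an unadjusted two-sample comparison with no stratum term.

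**Case A: both factors balanced by design, analysis unadjusted.** Let R² be the share of change-score variance that site and chemotherapy explain together. The documents give no value, so 0 to 0.10 is an assumption. Write f = √(1 − R²).

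- Nominal SE = 10 × √(2/122) = 1.280; true SE = 1.280 × f.
- Actual alpha of the unadjusted test = 2 × [1 − Φ(1.96 / f)].
- Power unadjusted = Φ[(3.6/1.280 − 1.96) / f].
- Power adjusted = Φ[3.6/(1.280 f) − 1.96].
- Extra patients the unadjusted test needs to match the adjusted power: with 3.6/1.280 = 2.812, this is [(2.812 + 1.96(1 − f)) / 2.812]² − 1.

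| Assumed R² | True SE | Actual alpha | Power unadjusted | Power adjusted | Worth in patients |
|---|---|---|---|---|---|
| 0 | 1.280 | 0.050 | 0.803 | 0.803 | 0 |
| 0.02 | 1.268 | 0.048 | 0.805 | 0.811 | 1.4% |
| 0.05 | 1.248 | 0.044 | 0.809 | 0.822 | 3.6% |
| 0.10 | 1.215 | 0.039 | 0.815 | 0.842 | 7.3% |

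A simulation agrees (244 patients, one binary factor at 50%, blocks of 4 within strata, 5,000 runs per setting). For R² of 0.02, 0.05 and 0.10, the unadjusted type I error was 0.049, 0.041 and 0.038; adjusted, it was 0.051, 0.046 and 0.048.

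**Case B: only site blocked, chemotherapy left to chance.** Assume that a proportion p of 30-50% had chemotherapy and that chemotherapy shifts FACIT-F change by 2-5 points. Neither figure is in the documents. With 122 analysed per arm:

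- SD of the between-arm gap in chemotherapy share = √(2p(1 − p)/122) = 5.9 points (p = 0.3) to 6.4 points (p = 0.5).
- Probability of a gap above 10 points: 9% to 12%.
- 95% limit = 1.96 × SD = 11.5 to 12.5 points.
- Shift in the estimate at that limit: from 0.115 × 2 = 0.23 to 0.125 × 5 = 0.63, that is 0.2-0.6 points against the 3.6-point target.

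Simulated without balancing the factor, the unadjusted test had type I error of 0.048-0.053 across the same R² values, which is nominal within simulation error. Cases A and B are alternatives and do not add.

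**The case against.** The strongest reply is that nothing here is contradictory or harmful. Most of it stands.

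- **A reader might infer that the two sections conflict.** Neither says its factor is the only one. Section 4.3 gives a mechanism and 12.3 a factor, and blocks within site-by-chemotherapy strata satisfy both. The documents do not show how the list was built. What remains is that neither section states the combined scheme and the operational one omits chemotherapy.
- **A reader might infer that the primary analysis is deliberately unadjusted.** The documents name no primary model; they do not exclude covariates. Section 12.3 could even mean a stratified analysis. Only the sample-size arithmetic is demonstrably unadjusted.
- **A reader might infer that the error rate is inflated, the sample size wrong, or the benefit of stratifying lost.** None of these follows. Alpha stays at or below 0.05 in Case A. Power at 122 per arm stays above 0.80. Balance lowers the true variance even when the test ignores it, so unadjusted power rises slightly with R².
- **A reader might price adjustment at 1/(1 − R²) − 1, that is 2.0-11.1% more patients.** That treats stratification as having gained nothing. With balanced strata the figure is 1.4-7.3%.
- **A reader might call the 0.2-0.6 point shift bias.** It is chance imbalance at a 95% limit, and the unadjusted standard error already covers it.

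The prognostic premise is also thin. The cited cohort concerns fatigue level during radiotherapy, in a paragraph that stresses conflicting findings. The primary outcome is change after randomisation in patients already selected for a drop of at least 10 points (Section 3.3.7). If R² is zero, nothing changes.

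**Conclusion.** The point holds as a clarification with a small gain in precision. The randomisation scheme is incompletely specified across Sections 4.3 and 12.3, and the primary comparison does not say that the randomisation factors will be used.

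With balanced factors and an assumed R² of 2-10%, adjusting restores the nominal alpha and raises power by about 0.005 (0.805 to 0.811) to 0.027 (0.815 to 0.842). If only site is blocked, adjustment for chemotherapy would remove a chance shift of up to about 0.2-0.6 points at the 95% limit, under assumed prevalence and effect.

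The text is clear on which factors are named where. The size is less certain, because R², chemotherapy prevalence and chemotherapy effect are all assumptions. The documents do not support reading this as an inflated type I error, a biased estimate or an inadequate sample size.

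**What to change.** - In Sections 4.3 and 12.3, state the same scheme: permuted blocks within the four strata formed by site (DFCI/BWH, MGH) and chemotherapy (yes, no).
- In Section 12.1, state that the between-arm difference in FACIT-F change is estimated from a linear model containing treatment, site and chemotherapy as recorded at randomisation.
- If the list was already built by site only, keep it and still enter chemotherapy as a covariate, fixed before unblinding.

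The cost is a few sentences and no extra patients. The appended patient and clinical forms contain no direct yes/no item for chemotherapy, and the eligibility checklist is not shown, so one field may need adding at registration. The timing matters: a list cannot be rebuilt once patients are randomised, and a covariate chosen after unblinding is open to challenge.
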